exam to evaluate the potential subject's optic nerve. Photographs (external, eye movements, optic nerve) may be taken as needed. This eye examination is standard of care on any thyroid eye disease patient. Findings from the eye exam will be used to determine a CAS and VISA score. The CAS takes into account 7 manifestations (spontaneous retrobulbar pain, pain with eye movement, eyelid erythema, eyelid edema, conjunctival injection, chemosis, and caruncular swelling) with 1 point assigned for each positive finding. The VISA score ranges from 0-16 based on findings related to inflammation, strabismus, and eyelid changes and proptosis (appearance). Both scales were developed to assess features of active disease that might change with treatment.

- Study subjects will be randomly assigned to observation with no prescription treatment, or treatment with oral celecoxib 100 mg twice daily for 3 months. Patients will have a full clinical exam at baseline, 1 month, 3 months, 6 months, and 12 months, with additional clinical visits more frequently if indicated by disease course/activity. The proposed frequency of clinic visits is within standard of care for newly diagnosed active-phase TED.
- For those subjects randomized to the treatment group, baseline blood testing for blood counts, renal and hepatic function (BUN, Cr, AST, ALT, total bilirubin) will be obtained prior to starting the drug. Testing will be performed by a standard clinical laboratory and billed to insurance. Testing will be repeated at 1mo and 3mo after randomization/initiation of therapy for those receiving celecoxib. Abnormal BUN or creatinine (outside normal range) on lab testing or any previous/current kidney disease will be the criteria for labeling a patient as having impaired renal function. Abnormal liver enzymes (AST, ALT, bilirubin outside normal range) or previous/current liver disease will determine whether a patient is labeled as having impaired hepatic function. Monthly phone interviews also will be conducted by physician study team members to determine if other side effects, such as edema, may be occurring. Subjects will be asked specifically about peripheral swelling, any blood in urine or skin discoloration, or changes in exercise tolerance. Positive responses will trigger an unscheduled visit with the PI or co-investigator MD. Patients will be cautioned not to take additional NSAID medications while on Celecoxib, as this may increase the chance for adverse effects.

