- Outcomes: The primary study outcome is reduction of clinical activity of TED, as determined by both the CAS and VISA scores. We will use both scales because there is currently disagreement as to which scale serves as a better overall assessment tool. Secondary outcome measures will include reduction of specific aspects of TED, including proptosis, diplopia, and eyelid retraction, as well as a validated TED-specific quality of life survey. These elements are captured in part by the 2 scales but also will be evaluated separately. Comparison of our primary and secondary outcomes between the treatment and control groups and with published studies of steroid treatment for TED may provide us with an indication of the relative efficacy of celecoxib treatment and whether further study is warranted. Treatment safety also will be assessed, and adverse events recorded. A recent prospective study of intravenous corticosteroid dosing for TED reported major adverse events in 10/159 (6.3%) of subjects and minor adverse events such as gastric distress, mild BP increase not requiring medication, and local skin reactions in about 25% of subjects. We anticipate a lesser incidence of minor or major adverse events based on the side effect profile of celecoxib in patients without co-morbidities placing them at higher risk (most TED patients are young and otherwise healthy). Occurrence of adverse events at a rate

greater than what has been reported for intravenous corticosteroid (an accepted method of TED treatment) would suggest that risk of celecoxib treatment exceeds any benefit.

- Biospecimens will be collected in this study, to include urine for a pregnancy test for female patients of childbearing age to determine eligibility, as well as blood as noted above that will be drawn by the clinical lab.
- Study length: Subjects will be followed for 12 months.
- Safety monitoring: As noted, baseline blood testing and phone surveillance will be performed. If abnormal results are found during drug treatment, then subjects will be advised to stop the medication and will be examined by the PI or other MD investigator. Adverse events will be reported to the IRB per institutional policy.
- Subjects may be taken out of the study if:
 - Staying in the study would be harmful.
 - Treatment required is not allowed in the study.
 - Those that fail to follow instructions.
 - Subjects become pregnant.
 - The study is cancelled.

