 - There may be other reasons to take subjects out of the study that we do not know at this time.

5. Inclusion/Exclusion Criteria

Eligibility criteria:

- *Recent diagnosis of thyroid eye disease (within the past 6 months)*
- Have ocular symptoms or signs of TED with a CAS score of at least 3
- Ages 18-80 years

Exclusion criteria:

- Pregnancy
- Previous treatment with corticosteroid for TED for >2wks
- Previous treatment with orbital radiation for TED
- Impaired renal function
- Impaired hepatic function
- *Treatment with antihypertensive medications except beta-blockers*
- History of congestive heart failure, cardiac valvular disease, or coronary artery disease
- Allergy to NSAID or previous adverse reaction (ie. GI bleeding)
- Vision loss due to compressive optic neuropathy

Target 40 participants will be enrolled in this study.

6. Drugs/ Substances/ Devices

Celecoxib (Celebrex) is a non-steroidal anti-inflammatory drug approved by the Food and Drug Administration (FDA) for the treatment of pain, osteoarthritis, rheumatoid arthritis, and ankylosing spondylitis. We will be using the recommended dosage of 100 mg twice a day over the course of 3 months. Celecoxib for TED is an off-label usage.

7. Study Statistics

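### The labs behind the renal and hepatic exclusions are drawn only after randomisation and only in the celecoxib arm, and the plan does not say whether flagged subjects stay in the comparison

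*Combined protocol and SAP*

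**What the plan says.** Section 5 lists impaired renal function and impaired hepatic function among the exclusions, for every participant. Section 4 (Study Procedures) supplies the definitions. For the kidney: "Abnormal BUN or creatinine (outside normal range) on lab testing or any previous/current kidney disease will be the criteria for labeling a patient" as impaired. For the liver: "Abnormal liver enzymes (AST, ALT, bilirubin outside normal range) or previous/current liver disease". Each definition therefore has a history half and a laboratory half.

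The history is part of the examination planned for all patients. The laboratory panel is not. After describing random assignment, Section 4 orders it in these terms: "For those subjects randomized to the treatment group, baseline blood testing for blood counts, renal and hepatic function", to be obtained before the first dose. The follow-up panels are limited in the same way: "Testing will be repeated at 1mo and 3mo after randomization/initiation of therapy for those receiving celecoxib". No section plans blood tests before randomisation or in the observation arm. The only specimen tied explicitly to eligibility is the urine pregnancy test.

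On consequences, the safety-monitoring bullet says "If abnormal results are found during drug treatment, then subjects will be advised to stop the medication" and will be examined. It covers results during treatment, not the baseline panel. The general rule on duration is "Subjects will be followed for 12 months". The list of reasons for removal names no laboratory value, but it includes "Staying in the study would be harmful" and ends with "There may be other reasons to take subjects out of the study that we do not know at this time". Section 7 compares CAS and VISA changes between the two groups without defining who is counted.

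**The concern.** An eligibility criterion is normally settled before assignment, so that whatever it removes is removed from both future arms alike. Here half of two criteria can be assessed only once the arm is known, and only in one arm. A subject with raised creatinine who draws celecoxib can be found ineligible. The same subject drawing observation will not be, unless the history reveals kidney disease.

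If flagged subjects are then removed, or left out of the comparison, the loss comes from the celecoxib arm alone and the groups are no longer those that randomisation produced. The control is observation with no prescription treatment, and no masking is described. A decision on whether to count a flagged subject could therefore be taken with the assignment known. With a target of 40 participants, even one or two such decisions are a visible share of an arm.

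**Working it through.** **1. What the text settles and what it leaves open**

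| Step | Celecoxib arm | Observation arm |
|---|---|---|
| History of kidney or liver disease (Section 4) | taken | taken |
| Baseline panel (Section 4) | after assignment, before first dose | none planned |
| Panels at 1 and 3 months (Section 4) | yes | none planned |
| Lab-based exclusion possible (Sections 4 and 5) | yes, after randomisation | no |
| Stated action, abnormal baseline panel | none | not applicable |
| Stated action, abnormal result on treatment | advice to stop, examination | not applicable |
| Counted in the Section 7 comparison if flagged | not stated | not applicable |

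The one-arm testing is a stated rule. The removal of flagged subjects is not stated; it is what applying the Section 5 exclusion would mean.

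**2. How often the question would arise**

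The plan gives no flag rate, alpha, power, effect size or standard deviation, so there is no planned figure to reproduce. Assumptions: 1:1 allocation (20 of the 40 on celecoxib) and a flag probability p per subject at the baseline draw. As a guide to p, take healthy subjects, reference ranges covering the central 95%, and only high values counted:

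- all five tests fully correlated: p = 0.025, so 20 × 0.025 = 0.5 expected flags
- two independent tests (BUN and creatinine): p = 1 − 0.975² = 0.049, so 20 × 0.049 = 1.0
- five independent tests: p = 1 − 0.975⁵ = 0.119, so 20 × 0.119 = 2.4

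The chance of at least one flag among 20 is 1 − (1 − p)²⁰, which is 40% at p = 0.025, 64% at p = 0.05 and 92% at p = 0.119. The observation arm has no panel, so its expected number of lab flags is 0.

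**3. What it costs to keep flagged subjects in the comparison**

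For scale, take an effect that has 80% power with 20 per arm (two-sided t-test, alpha 0.05). That is a standardised difference d = 0.909. If a fraction p of the celecoxib arm gets no drug and no benefit but is still counted, the expected difference becomes d × (1 − p). If these subjects are left out, d is unchanged but the arm shrinks to 20 × (1 − p).

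| p | d × (1 − p) | Power, kept in untreated | Celecoxib n if left out | Power, left out |
|---|---|---|---|---|
| 0.025 | 0.886 | 78% | 19.5 | 79% |
| 0.05 (1 of 20) | 0.864 | 76% | 19.0 | 79% |
| 0.119 | 0.801 | 69% | 17.6 | 77% |

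The kept-in column holds the standard deviation fixed and assumes no drug at all. A subject who stops after the month-1 panel has had about a third of the 3-month course, so the figures overstate dilution for that case.

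**The case against.** The strongest reply is that the plan never says a flagged subject is removed. Follow-up is 12 months by default, and the stated response to an abnormal result on treatment is to stop the drug and examine the patient. Without removal or omission from the analysis there is no bias. This stands, and it is why the point is conditional. It does not dispose of the matter, because Section 5 makes the condition an exclusion, the removal list leaves room for discretion, and Section 7 does not say who is counted.

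A reader might infer that lab-triggered stops in one arm are themselves a flaw. They are not. Observation subjects have no study drug to stop, and monitoring only those exposed is reasonable. The month-3 panel falls at the end of the course, so it can hardly cause a stop at all.

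A reader might also try to state the bias as a shift in CAS points. The documents do not support one. The rates in step 2 describe chance flags in healthy subjects, and omitting subjects flagged purely by chance would not shift the mean systematically. A shift needs flagged subjects to have a different CAS change from the rest, and the documents give no figure for that.

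It is also fair to say that keeping flagged subjects in costs more power than leaving them out (69% against 77% at the highest rate shown). That is the price of a comparison that stays as randomised.

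Finally, the range wording has no direction, so a low AST or bilirubin would literally count as impairment. Physicians are likely to ignore such values, so this is a wording matter and not part of the main point.

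**Conclusion.** The point holds, at minor severity. As written, the lab half of the renal and hepatic exclusions can act only after assignment and only on the celecoxib arm. The plan does not settle whether a subject caught this way leaves the study or the comparison. If so, the comparison is no longer as randomised; if not, there is no such bias. The direction and size of any bias cannot be derived from the documents.

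What can be given is a scale for how often the question would arise: about 0.5 to 2.4 of 20 celecoxib subjects at baseline. This assumes 1:1 allocation, healthy subjects, central-95% ranges and high values only. The history half of each definition applies to both arms and is not in question.

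**What to change.** **Main change.** State in Sections 4, 5 and 7 that a subject found after randomisation to have an abnormal panel is kept off celecoxib, or stops it, but remains in 12-month follow-up and in the as-randomised comparison of CAS and VISA change. Section 5 needs the sentence too; otherwise such a subject would still meet a listed exclusion. Report the number of flags. This costs a sentence in each place and no loss of safety, since the drug is still withheld or stopped. The downside is the dilution shown above: at 1 of 20 flagged and untreated, about 76% power where full treatment would give 80%.

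**Alternative.** Draw the baseline panel in all candidates before randomisation. Lab exclusions then precede assignment, the eligibility mismatch disappears, and so does the baseline part of the dilution. The cost is about 20 more panels. Under Section 11 these would be charged to insurance, for subjects who then receive no study drug. The main sentence is still needed for results found on treatment.

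**Wording.** Define impairment for BUN, creatinine, AST, ALT and bilirubin as a value above the upper limit of normal. Leave blood counts two-sided. This removes needless low flags but does not cure the one-arm testing, because high values would still be found only in the celecoxib arm.

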- In addition to cytokines, activated T-cells produce ligands for peroxisome proliferator activated receptor (PPAR) gamma. These ligands include prostaglandins created via the cyclooxeganse-2 (COX-2) pathway. PPAR-gamma activation has been implicated in systemic adipogenesis in patients taking thiazolidinedione drugs for glycemic control, and *in vitro* studies of cultured orbital fibroblasts have shown that exposing cells to PPAR-gamma ligands such as specific prostaglandin analogues results in transformation of fibroblasts into adipocytes. This effect is more robust with TED fibroblasts than in cells isolated from control patients. Inhibiting the PPAR-gamma pathway *in vitro* with a selective COX-2 inhibitor blocks fibroblast transformation. A single case report in the literature also supports the possible *in vivo* efficacy of COX-2 inhibition in active TED.
- Based on these *in vitro* and *in vivo* findings, we propose to treat a cohort of patients with active TED using a selective COX-2 inhibitor, celecoxib (Celebrex), and to compare these patients to an observational control group. We hypothesize that celecoxib will reduce the severity of disease and/or prevent progression to proptosis, diplopia, and corneal exposure or compressive optic neuropathy. We will assess the effect of the treatment using validated clinical scoring tools, including the Clinical Activity Scale (CAS) from the European Graves Orbitopathy Group (EUGOGO) and the VISA (vision, inflammation, strabismus, appearance) scale of the International Thyroid Eye Disease Study (ITEDS) group. We will also use a validated Graves ophthalmopathy quality of life survey as a secondary outcome measure. Outcomes will be assessed at timepoints noted below with a 3-month period of treatment and follow-up for 1 year.

4. Study Procedures

- Patients will be recruited from the Wilmer Eye Institute practices of the investigators.
- The exam will include a thorough history including a list a medications, health conditions previous surgeries and medical allergies (standard of care).
- The complete eye examination will measure visual acuity, eye movements (sensorimotor exam), visual fields, proptosis, pupil function, anterior segment evaluation, and lastly dilated fundus

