The primary study outcome is reduction of clinical activity of TED, as determined by both the CAS and VISA scores. We will use both scales because there is currently disagreement as to which scale serves as a better overall assessment tool. Secondary outcome measures will include reduction of specific aspects of TED, including proptosis, diplopia, and eyelid retraction. These elements are captured in part by the 2 scales but also will be evaluated separately. Change in quality of life will be measured by a validated questionnaire as another secondary outcome measure. Comparison of our primary outcomes between treatment and control groups will provide us with an indication of the relative efficacy of celecoxib treatment. Treatment safety also will be assessed, and adverse events recorded. A recent prospective study of intravenous corticosteroid dosing for TRO reported major adverse events in 10/159 (6.3%) of subjects and minor adverse events such as gastric distress, mild BP increase not requiring medication, and local skin reactions in about 25% of subjects. We anticipate a lesser incidence of minor or major adverse events based on the side effect profile of celecoxib in patients without co-morbidities placing them at higher risk (most TED patients are young and otherwise healthy). Occurrence of adverse events at a rate greater than what has been reported for intravenous corticosteroid (an accepted method of TED treatment) would suggest that risk of celecoxib treatment exceeds any benefit. Observation of adverse events in excess of this rate during the treatment phase would require review, and consideration of early study termination. The changes in either the CAS or VISA score will be compared between the celecoxib and observation groups to determine whether a trend or significant difference can be found.

8. Risks

The study procedures, apart from the proposed treatment, carry no risk beyond that of standard clinical care. Celecoxib has well-described risks especially in certain patient populations, who will be excluded from this study as noted. Below is an enumeration of risks copied from the package insert:

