- **Cardiovascular warning:** All prescription NSAIDs, like CELEBREX, ibuprofen, naproxen, and meloxicam have the same cardiovascular warning. They may all increase the chance of heart attack or stroke that can lead to death. This chance increases if you have heart disease or risk factors for it, such as high blood pressure or when NSAIDs are taken for long periods. Congestive heart failure and peripheral edema has also occurred in some patients has also been noted.
- CELEBREX should not be used right before or after certain heart surgeries.
- Stomach and intestine risk: All prescription NSAIDs have the same warning for serious stomach and intestine problems: They may cause ulcers and bleeding, which can occur without warning and may cause death.
- **Renal warning:** Long term use of NSAIDs, like CELEBREX, have resulted in renal papillary necrosis. Patients at risk are those with impaired renal function, heart failure, liver dysfunction, those taking diuretics, ACE inhibitors, and angiotension II inhibitors.

Date: January 21, 2017 Principal Investigator: [name] Application Number: IRB00094787

• Serious skin and allergic reactions can occur with CELEBREX. CELEBREX shold not be taken if one has had an asthma attack, hives, or other allergies to aspirin, other NSAIDs, or certain drugs called sulfonamides.

Risks of corticosteroid treatment are noted in section 7 with at least 25% of patients experiencing a minor or major adverse event. Orbital radiotherapy carries theoretic risk of ocular radiation toxicity (cataract formation, radiation retinopathy or optic neuropathy) and second malignancy occurrence, but the actual rate of such events is not known. Untreated, some patients with TED may have spontaneous improvement while others will progress to more severe manifestations. Increased disease activity at presentation is a predictor for progression, and we thus are including only subjects with clinical activity that may put them at risk for such changes. Treatment is effective only during the active phase of TED, and observation may result in irreversible proptosis or strabismus requiring subsequent surgery.

9. Benefits

The major benefit of the study is anticipated to be reduction of TED severity as measured by clinical activity assessment.

10. Payment and Remuneration

Subjects will not be compensated for participation.

11. Costs

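### The named safety-call questions omit gastric, GI-bleeding, chest-pain and stroke symptoms and no blood-pressure reading is specified, so the adverse-event rate that Section 7 compares with a steroid benchmark may be under-counted

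*Combined protocol and SAP*

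**What the plan says.** Section 4 (Study Procedures) gives the purpose of the calls: "Monthly phone interviews also will be conducted by physician study team members to determine if other side effects, such as edema, may be occurring". It then names the items: "Subjects will be asked specifically about peripheral swelling, any blood in urine or skin discoloration, or changes in exercise tolerance". The consequence follows: "Positive responses will trigger an unscheduled visit with the PI or co-investigator MD".

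The other specified safety measure is laboratory work in the celecoxib arm: "baseline blood testing for blood counts, renal and hepatic function (BUN, Cr, AST, ALT, total bilirubin) will be obtained prior to starting the drug", repeated at 1 and 3 months. The safety-monitoring item later in Section 4 refers back to blood testing and phone surveillance and adds no further method of detection. It does say that abnormal results during treatment lead to advice to stop the drug and to an examination by a physician investigator.

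A full clinical examination is scheduled at baseline and at 1, 3, 6 and 12 months. Where its content is itemised, it is a history and ocular measures: "The complete eye examination will measure visual acuity, eye movements (sensorimotor exam), visual fields, proptosis, pupil function, anterior segment evaluation", followed by a dilated fundus examination. Blood pressure is not listed there or anywhere else.

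Section 8 (Risks) says of NSAIDs as a class, on cardiovascular events, "They may all increase the chance of heart attack or stroke that can lead to death", and on the gut, "They may cause ulcers and bleeding, which can occur without warning and may cause death".

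Section 7 (Study Statistics) takes its safety benchmark from a study of intravenous corticosteroid: major events in 10/159 (6.3%), and "minor adverse events such as gastric distress, mild BP increase not requiring medication, and local skin reactions in about 25% of subjects". A celecoxib rate above the benchmark during treatment is to prompt review and possible early termination.

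**The concern.** The protocol chose to name specific questions, but those it named do not match its gravest warnings. They fit the oedema, renal and skin risks. The gut has no named question. The heart has only indirect prompts (exercise tolerance and swelling), and stroke has none.

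The same gap affects the trial's safety comparison. The benchmark's named minor events are gastric distress, mild blood-pressure rise and local skin reactions. The first has no prompt. The second usually causes no symptom, so it needs a reading that the plan does not specify. If such events occur and are missed, the celecoxib count falls, celecoxib looks safer against the external figure, and the Section 7 review becomes less likely. Because the comparator is a published rate, equally limited collection in the observation arm would not correct this.

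**Working it through.** **Step 1. The plan's own figure.** 10/159 = 0.0629, which rounds to the stated 6.3%. The documents contain no sample-size or power calculation to reproduce.

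**Step 2. Risks and benchmark events against specified detection.**

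| Event | Where named | Specified means of finding it |
|---|---|---|
| Heart attack | Section 8, potentially fatal | Exercise tolerance and swelling, as indirect prompts; no chest-pain question |
| Stroke | Section 8, potentially fatal | None named |
| Ulcers, GI bleeding | Section 8, potentially fatal | No named question; blood counts at months 1 and 3 may show blood loss |
| Renal injury, oedema | Section 8 | Blood in urine, swelling, renal tests |
| Skin and allergic reactions | Section 8 | Skin discoloration, in part |
| Gastric distress | Section 7 benchmark | None named |
| Mild blood-pressure increase | Section 7 benchmark | None specified |
| Local skin reactions | Section 7 benchmark | Skin discoloration, in part |

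Two of the three named benchmark minor events therefore have no specified means of detection.

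**Step 3. What under-detection would do to the trigger.** This step is an illustration.

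Inputs from the documents: 40 participants (Section 5); minor benchmark about 25% and major benchmark 6.3% (Section 7).

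Assumptions: 20 treated (1:1; the ratio is not stated); the true celecoxib event rate p; the share c of events captured; and a trigger read as any observed rate above the benchmark. The smallest count above 25% of 20 (= 5) is 6. The smallest count above 6.3% of 20 (= 1.26) is 2.

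Formula: P(trigger) = P(X ≥ r), with X ~ Binomial(20, p × c).

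| True rate p | r | c = 1 | c = 0.80 | c = 0.67 | c = 0.50 |
|---|---|---|---|---|---|
| 25% minor | 6 | 38.3% | 19.6% | 10.4% | 3.1% |
| 35% minor | 6 | 75.5% | 50.5% | 32.1% | 12.2% |
| 40% minor | 6 | 87.4% | 65.7% | 45.6% | 19.6% |
| 15% major | 2 | 82.4% | 71.1% | 61.1% | 44.9% |

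For example, at p = 40% and c = 0.50 the observed rate is 0.40 × 0.50 = 0.20, and P(X ≥ 6) = 19.6%.

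**Step 4. Sensitivity to the number treated, at p = 40%.** With 13 treated (r = 4) the chance is 83.1% with full capture and 25.3% with half. With 27 treated (r = 7) it is 95.8% and 28.7%. The fall is of the same order whatever the split.

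**The case against.** A reader might infer that the potentially fatal risks are simply not asked about. The documents do not support that. The calls are made by physicians, and their stated purpose extends to side effects in general, with oedema as an example. Adverse events are also to be recorded generally. A patient could volunteer stomach pain or chest pain. What stands is that no prompt is named for these symptoms and no method of eliciting them is described.

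Nor can a patient who answers no to every question go unseen throughout treatment: examinations and blood tests fall at months 1 and 3 of a 3-month course. Section 5 also excludes heart failure, valvular or coronary disease, previous GI bleeding on an NSAID and most antihypertensive treatment. These safeguards lower the risk, but they do not measure blood pressure or detect gastric distress.

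Three further readings go too far. Bleeding is not wholly omitted, because blood in urine is asked about; it is GI bleeding that is missing. Asthma appears in Section 8 as a reason not to take the drug and is not called fatal. And it cannot be said that no visit measures blood pressure, only that no visit is specified to do so; the full clinical examination is not itemised beyond the history and eye measures.

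The strongest objection concerns bias. To say that the rate is biased low relative to the benchmark, one must know how the corticosteroid study collected its events, and the documents do not say. If that study relied on volunteered reports, prompted questions here could tilt the comparison the other way. The benchmark's minor events are also only examples, for a different drug, and say nothing about the mix of events on celecoxib. So under-counting is possible, not shown.

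Finally, the trigger is weak for another reason. At a true rate of exactly 25% with full capture, 6 or more of 20 still occurs 38.3% of the time. Better questions do not cure a small sample.

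**Conclusion.** The concern holds as a mismatch between what Section 4 specifies, the risks Section 8 describes and the benchmark Section 7 uses. Followed as written, the plan has no specified way to detect a symptomless blood-pressure rise and no prompt for gastric, GI-bleeding, chest-pain or stroke symptoms. The celecoxib rate may therefore be under-counted, and the Section 7 review may be triggered less often than it should be.

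Missing events can only lower the observed count. How many would be missed cannot be determined from the documents, and neither can the net effect on the comparison with the benchmark. The fall from 87% to 46% or 20% rests on an assumed 20 treated, an assumed 40% true rate and assumed capture fractions. It shows how sensitive the trigger is and does not estimate what would happen in this trial. The point should be addressed, but it does not show that safety monitoring is absent.

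**What to change.** In Section 4, add to the existing monthly calls questions on gastric symptoms, GI bleeding, chest pain, stroke symptoms and allergic symptoms. Specify a blood-pressure reading at the existing baseline, 1-month and 3-month visits. In Section 7, state that events found this way count in the rate compared with the benchmark. If the benchmark study's method of collecting events is known to the investigators, state it beside the 25% figure so that the comparison can be read fairly.

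The interview and safety-monitoring text of Section 4 should be reconciled with Sections 7 and 8 on what follows a positive response to each question. That is a clinical rule for the investigators to settle, and none is proposed here.

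The cost is a few minutes per contact and a cuff reading at three visits already planned. The adverse-event count may rise, which is a consequence of fuller collection and should be expected when the rate is read against the benchmark.
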